7.3 B - AF-related symptoms

Before enrollment, subjects are queried about the absence or presence of each of the following AF-related symptoms:

- Palpitations, i.e., sensation of a racing, uncomfortable, irregular heartbeat or a flipflopping in your chest
- Lightheadedness or dizziness
- Shortness of breath or dyspnea
- Chest discomfort

At 30, 60, and 90 minutes post dose, subjects are again queried about each of these individual symptoms in terms of "no symptoms, improved, unchanged or worsened" as compared to baseline.

During the Day 2 and Day 5 telephone assessments, the subject is again queried on the status of each of these individual AF symptoms as compared to baseline.

7.4 B - Treatment satisfaction questions

After 90 minutes post dose and prior to discharge, subjects whose AF converted to SR due to study drug (i.e., converted within 90 minutes post dose without any alternative treatment) are asked the following questions regarding their treatment satisfaction:

- o If offered, would you take the study treatment again in the future?
- On a scale of 1 to 10 (1 being very dissatisfied and 10 being very satisfied), how satisfied were you with the study treatment?

7.5 B - Study endpoint(s)

7.5.1 B - Primary endpoint

The primary efficacy endpoint is the proportion of subjects whose AF converted to SR by inhaled flecainide within 90 minutes after initiation of dosing. Conversion of AF to SR is defined as the presence of SR lasting for at least 1 minute.

7.5.2 B - Secondary endpoints

The secondary efficacy endpoints are:

The proportion of subjects with C_{max} values ≥ 200 ng/mL (e.g., 200, 300, 400, and 500 ng/mL) post inhalation with inhaled flecainide (excluding plasma levels associated with IV flecainide infusion) whose AF converted to SR by inhaled flecainide within 90 minutes after initiation of dosing.

Study no. FLE-002

Version 8.0 EU-1 Page: 63 of 117

- The time to conversion of AF to SR from initiation of dosing up to 90 minutes after initiation of dosing;
- The proportion of subjects in SR on Day 2;
- The proportion of subjects with reduced or no AF symptoms at 30 minutes post dose;
- The proportion of subjects with reduced or no AF symptoms at 60 minutes post dose;
- The proportion of subjects with reduced or no AF symptoms at 90 minutes post dose;
- The proportion of subjects who had their AF converted to SR within 90 minutes after initiation of dosing and had no AF recurrence requiring electrical or pharmacological cardioversion or rate control intervention, up to discharge;
- The proportion of subjects in SR on Day 5.

Time to conversion will be reported in statistical analyses from both initiation of study drug and completion of study drug.

The secondary safety endpoint is the incidence of treatment emergent serious adverse events of interest for flecainide

7.5.3 B - Exploratory endpoints

The exploratory endpoints (for the HHE) are:

- Proportion of subjects for whom capture and assessment of a diagnostic echocardiogram using a HHE at screening was successful
- Percent of subjects who are considered ineligible for enrollment as a result of the HHE assessment
- Time from HHE administration to availability of HHE report/results

The HHE data will be submitted to an independent reviewer to compare with the HHE assessments made by the site staff during the screening period; however, this independent review will not be used for the assessment of subject eligibility during screening. This independent review will only be used to explore if site staff made a successful assessment of subject eligibility using the HHE data obtained during screening.

8 B - Other assessments

8.1 B - Pharmacokinetic (PK) assessment(s)

Whole blood samples of about 4.0 mL are collected for measurement of plasma concentrations of flecainide acetate components as specified in the Schedule of Assessments (Section 17.4). Dense sampling occurs only over a 90-minute period on Day 1 (day of dosing).

Study no. FLE-002

Version 8.0 EU-1 Page: 64 of 117

Sample collection times are as follows:

- 1. Pre-dose inhalation: T_{Pre} (any time up to 45 minutes prior to dosing and after treatment assignment)
- 2. During dose regimen administration: T_{between admin} (in the 1-minute break in between inhalations), if applicable
- 3. At the time of conversion to SR: T_{SR}. A PK sample shall be taken at SR regardless of method of conversion. If conversion is, for example, by ECV, the PK sample should be taken at the earliest time feasible.
- 4. After administration of the study drug regimen is complete: T_x (1, 3, 10, 30, 60 and 90 minutes post dose).

When time points coincide for blood draw and vital signs assessments, procedures should be performed in said order.

Instructions for the collection, processing, storage and shipping of biological samples are provided in the Laboratory Manual.

Plasma samples are assayed by a validated LC/MS/MS method, which is specific for the determination of flecainide acetate components and used to evaluate the PK parameters.

No genetic analyses are to be performed on these plasma/whole blood samples.

Subject confidentiality is maintained at all times.

The Institutional Review Board (IRB)/Independent Ethics Committee (IEC) are informed of any safety issues that require alteration of the safety monitoring scheme or amendment of the IC.

8.2 B - Pharmacodynamic (PD) assessment(s)

To evaluate the electrocardiographic effects of inhaled flecainide under oral inhalation dosing regimens in subjects with recent onset of paroxysmal AF, which are detectable on 12-lead ECG recordings mainly by assessing the following PD variables: PR, QRS, and QT intervals.

ECGs are reviewed by an independent ECG Core Laboratory. Triplicate ECGs will be extracted from the recorded AECG (Holter) data transmitted by the site to the ECG Core Laboratory according to the Schedule of Assessments (Section 17.4). 12-lead ECGs will be extracted at or after each specified time point (up to 5 minutes after the specified time point or up to the next scheduled time point, whichever comes first). The triplicate 12-lead ECG extractions are overread on the same lead by the same ECG Core Laboratory reader.

Extraction time points for ECG recordings under both regimens are as follows:

- 1. Pre-dose inhalation: T_{Pre} at -45, -30 and -15 minutes
- 2. Just before the start of inhalation: T_{Admin}

INSTANT Study Clinical Study Protocol

Study no. FLE-002

Version 8.0 EU-1 Page: 65 of 117

- 3. During dose regimen administration: T_{between admin} (in the 1-minute break in between inhalations)
- 4. At the time of conversion to SR: T_{SR}
- 5. After administration of study drug regimen is complete: T_x (1, 3, 10, 30, 60, and 90 minutes post dose)

Details of the ECG Core Laboratory analyses are included in the Core Laboratory analysis plan. At a minimum, the following ECG parameters are determined for each ECG recording:

- Heart rate (HR)
- RR interval
- PR interval
- QRS duration
- QTcF duration
- JTc duration (QTc-QRS)

ECGs extracted from the 12-lead Holter are provided to Investigators for filing in the subject's source records. Any original ECG recordings obtained at the site must also be stored in the subject's source records.

9 B - Safety evaluation and reporting

9.1 B - Adverse events

Refer to the definitions for AEs and SAEs in Section 17.2.1. The clinical safety of inhaled flecainide is evaluated by the frequency of treatment emergent AEs and SAEs. Treatment emergent SAEs (TESAE) are those SAEs defined as following dose administration.

Safety and tolerability of inhaled flecainide is further evaluated by collection of the following measurements performed according to the Schedule of Assessments (Section 17.4):

- Monitoring of AEs, SAEs and AEs/SAEs of special interest (AESIs/SAESIs)
- Physical examinations
- Vital signs (heart rate, systolic and diastolic blood pressure, respiratory rate and oxygen saturation)
- Routine ECGs or 10-second printouts of telemetry rhythm strip performed for safety purposes are printed and reviewed on-site
- Continuous telemetry
- Pulmonary function by lung auscultation and oxygen saturation
- Clinical local laboratory assessment (including hematology, comprehensive metabolic and coagulation panel)

Recurrent AF will not be considered an AE as it is an expected event in this patient population. Recurrence of AF will be captured in a separate eCRF.

INSTANT Study Clinical Study Protocol

Study no. FLE-002

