8.0 EU-1 Page: 68 of 117 Version

9.1.2.4 B – Serious Adverse Events of Special Interest (SAESI)

The following potential SAESIs are defined for study purposes:

- Hypotension, with symptoms/signs of clinical instability (i.e., severe chest pain/dyspnea or altered mental status), and requiring a vasopressor or inotropic agent
- Ventricular tachycardia, sustained (> 30 seconds or requiring intervention before that time) VT, TdP, or VF
- Bradycardia, with symptoms/signs of clinical instability (i.e., severe chest pain/dyspnea, altered mental status or hypotension), and requiring pacing or a chronotropic agent
- Sinus pauses post conversion of AF to SR, causing syncope, or requiring pacing or CPR
- Atrial flutter with 1:1 conduction with fast ventricular response (ventricular heart rate ≥ 200 bpm), and requiring intervention (DC cardioversion) for termination, or an IV AV nodal blocking agent (β-blocker or Ca2+-channel blocker) to slow the ventricular rate
- Any arrhythmia with symptoms/signs of clinical instability (i.e., severe chest pain/dyspnea, altered mental status or hypotension), and requiring DC cardioversion, defibrillation, pacing, or a vasopressor, inotropic or chronotropic agent

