9.1 C - Patient-Led Under Medical Supervision Cardioversion Study: adverse events

Adverse events for subjects participating in the study will be captured from time of consent until EOS. End of study coincides with Day 5 after the subject's treatment visit, or 8 months after signing consent, whichever comes first. All AEs, SAEs, and AESIs will be captured and reported in accordance with Section 9.1 B.

Recurrent atrial fibrillation will not be considered as an adverse event as it is an expected event in this patient population. AF recurrence will be captured in a separate eCRF.

INSTANT Study Clinical Study Protocol

Study no. FLE-002

Version 8.0 EU-1 Page: 90 of 117

9.2 C - Patient-Led Under Medical Supervision Cardioversion Study: clinical local laboratory assessments

Blood samples as described in Part B may be obtained on Day 1 prior to self-administration of the study drug per the discretion of the treating physician. The following laboratory assessments are required to confirm eligibility:

- serum creatinine
- serum potassium
- serum or urine pregnancy test (only for female subjects of child-bearing potential)

A blood draw for assessment of potassium must always be drawn on Day 1 prior to self-administration of study drug; however, if results are available for any or all other parameters from a blood draw up to 24 hours prior to Day 1, there is no need for a new blood draw for those parameters.

If laboratory values from non-protocol specified laboratory assessments performed at the site's local laboratory are considered clinically significant by the Investigator (e.g., AE or SAE), then the results must be recorded in the eCRF.

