17.2 Appendix 2: Adverse Events: Definitions and classifications of AE assessment

17.2.1 Definitions

17.2.1.1 Adverse Events

In the context of a clinical study, an AE is any untoward medical occurrence in a patient or clinical investigation subject administered a pharmaceutical product and which does not necessarily have to have a causal relationship with this treatment. An AE can therefore be any unfavorable and unintended sign (including an abnormal laboratory finding for example), symptom, or disease temporally associated with the use of a medicinal product, whether or not considered related to the medicinal product.

For the purposes of this study, a recurrence of AF will not be considered as an AE. Atrial fibrillation recurrence will be collected in a specific, designated eCRF.

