**FLE-002 (INSTANT) – Final Analysis****Statistical Analysis Plan****3.4 Adverse Events****Adverse Event**

An AE is any untoward medical occurrence in a patient or clinical study subject administered a pharmaceutical product and which does not necessarily have a causal relationship with this treatment. An AE can therefore be any unfavourable and unintended sign (including an abnormal laboratory finding for example), symptom, or disease temporally associated with the use of a (investigational) medicinal product, whether or not considered related to the (investigational) medicinal product.

All adverse events will be recorded on the Adverse Event electronic case report form (eCRF). For the purposes of this study, a recurrence of AF will not be reported as an adverse event. AF recurrence will be collected in a specific eCRF designed to capture this data. However, recurrences of AF that meet the definition of a serious adverse event (SAE) will be captured on the AE CRF.

For the definition of an SAE, please refer to protocol Section 17.2.1.2.

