**10 Difference between protocol and SAP**

The SAP is in accordance with study protocol V8.0/ EU-1 except for the following deviations:

- The SAP adds Methods for Cardioversion (refer to SAP section 3.2)
- The SAP specifies cohorts of the pre-specified study populations to be analyzed (refer to Table 1 in Section 8.0)
- Only 3 subjects were treated with study medication in the PLS study, as a result for some endpoints results are only listed and no summarizing statistics will be reported
- No HHE data are available for the PLS study, the endpoints will thus not be reported
- The protocol indicates a 90% confidence interval will be created for endpoints, instead (refer to SAP sections 9.2) for a selection of endpoints a 95% confidence intervals will be created; only for the primary efficacy endpoint (refer to SAP section 9.2.1) a 90% confidence interval will be created.
- The protocol indicated  $t_{max}$  is measured as the time to Cmax (from the time of end of dosing), in the SAP definition  $t_{max}$  is measured as the time to Cmax (from the time of the start of dosing).
- Adverse Events of Special Interest (AESI) and Serious Adverse Events of Special Interest (SAESI) will be tabulated using results as indicated in SAP section Annex A, using a slightly different definition than the definition in protocol V8.0/EU-1.

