**2. Purpose**

- 2.1 This document outlines the steps required to review all AEs reported in patients who received 120 mg FlecIH-103 in Parts A, B and C of the FLE-002 study to determine if they meet the final AESI criteria as defined in the protocol.
- 2.2 This review will generate data that is to be used in the final analysis of the study, as described in the FLE-002 Statistical Analysis Plan (SAP).

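### The protocol excludes all recurrent AF from adverse events, contradicting its own serious-AESI list and an undeclared SAP exception, so qualifying events may miss 24-hour reporting, the AE tables and the secondary safety endpoint

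*Protocol*

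**What the plan says.** Protocol 9.1 B, which also governs the Part C medically-led study (MLS), gives sites a flat rule: "Recurrent AF will not be considered an AE as it is an expected event in this patient population". It adds: "Recurrence of AF will be captured in a separate eCRF". Protocol 9.1 C repeats it for the patient-led study (PLS): "Recurrent atrial fibrillation will not be considered as an adverse event as it is an expected event in this patient population". The definitions appendix, 17.2.1.1, builds it into the meaning of an adverse event: "For the purposes of this study, a recurrence of AF will not be considered as an AE". None of these places makes an exception for a serious or unstable recurrence.

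The SAESI list in Protocol 9.1.2.4 B ends with a general item that begins "Any arrhythmia with symptoms/signs of clinical instability (i.e., severe chest pain/dyspnea, altered mental status or hypotension), and requiring DC cardioversion" and goes on to defibrillation, pacing and circulatory drug support. AF is not carved out. SAP 3.4 and Annex A 4.6 carry the same item.

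SAP 3.4 restates the exclusion and then qualifies it: "However, recurrences of AF that meet the definition of a serious adverse event (SAE) will be captured on the AE CRF". SAP 5.6.1 repeats the qualification and says that these events enter the AE summary tables. SAP section 10 opens with "The SAP is in accordance with study protocol V8.0/ EU-1 except for the following deviations", and the list that follows does not include this exception.

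The sponsor review that feeds the safety endpoint is set up in Annex A, section 2, to "review all AEs reported in patients who received 120 mg FlecIH-103 in Parts A, B and C".

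**The concern.** A subject may convert after dosing, relapse into AF, become unstable and need intervention. Under 9.1.2.4 B that is an SAESI. Under 9.1 B and 17.2.1.1 it is not an adverse event at all. No passage says which rule prevails.

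The choice matters because an event that never reaches the AE page has no stated route into the safety results. The secondary safety endpoint is the incidence of treatment-emergent SAESIs. It is the only secondary safety endpoint and its count may be close to zero, so a single unrecorded event could change what is reported. Capture could also differ between sites, depending on which passage each one followed.

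**Working it through.** The plan states no figure on this point, so there is none to reproduce. The check sets the rules side by side and then traces where the data go.

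**Step 1. What each rule does with a recurrence after conversion.**

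| Type of recurrence | Protocol 9.1 B, 9.1 C, 17.2.1.1 | Protocol 9.1.2.4 B | SAP 3.4, 5.6.1 | Agreement |
|---|---|---|---|---|
| Neither SAE nor SAESI criteria met | Not an AE | Not an SAESI | Not an AE | Yes |
| SAE criterion met, SAESI not met | Not an AE | Not an SAESI | AE form, tabulated as SAE | No |
| SAESI met, not classed as SAE | Not an AE | SAESI | Exception does not apply | No |
| Both met | Not an AE | SAESI | AE form, tabulated as SAE | No |

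The third row is a real possibility. Protocol 17.2.1.2 says that a hospital stay under 24 hours does not count as an SAE on the hospitalisation criterion, which leaves the life-threatening and medically-important criteria to judgement. An unstable recurrence treated and discharged the same day could meet 9.1.2.4 B without being classed as an SAE. The SAP exception is keyed to the SAE definition alone, so it would not bring that event in.

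**Step 2. What depends on the AE page.**

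- 24-hour reporting: Protocol 9.1.1 B ties it to SAEs recorded on the AE page of the eCRF, and 9.1.2 B has AESIs reported by entering them on that page.
- AE and treatment-emergent SAE tables: SAP 5.6.3 makes the Clinical AE database the sole source for Part B and Part C MLS subjects.
- Secondary safety endpoint: SAP 9.2.2.12 counts AEs that start between first inhalation and Visit 2 (Day 5) and that the sponsor classes as SAESI.
- Sponsor classification: Annex A 1.4, 2.1 and 5.1 work from a MedDRA-coded AE listing. The AF-recurrence form is not named.

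A site that applied 9.1 B literally would keep the event out of all four.

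**Step 3. Timing.** SAP V5.0 is dated 06 July 2022. SAP 1.1.1 gives the last MLS dosing as 07 December 2021. This SAP version therefore could not have instructed MLS sites while they were reporting. Earlier protocol and SAP versions, and the eCRF completion guidelines, are not available to check.

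**Step 4. Size of one omitted subject.** The SAP asks for counts and percentages for this endpoint; exact 95% (Clopper-Pearson) intervals are added here for scale. For 0 of n the upper limit is 1 − 0.025^(1/n). For 1 of n the lower limit is 1 − 0.975^(1/n) and the upper limit is the 97.5% quantile of a Beta(2, n − 1) distribution. The final safety N is not stated, so three values are shown.

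| n | Basis | 0 events | 1 event |
|---|---|---|---|
| 25 | Planned Part B | 0% (0 to 13.7) | 4.0% (0.1 to 20.4) |
| 54 | Assumed: 29 Part A FlecIH-103 + 25 Part B, no Part C | 0% (0 to 6.6) | 1.9% (0.0 to 9.9) |
| 100 | Assumed | 0% (0 to 3.6) | 1.0% (0.0 to 5.4) |

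**The case against.** The strongest reply is that no loss of events is shown. SAP 3.4 and 5.6.1 say that serious recurrences are captured and tabulated. Protocol 9.1.2.4 B is itself an instruction to sites: read with 9.1.1 B and 9.1.2 B, it can be taken to require 24-hour reporting of any unstable arrhythmia. The eCRF guidelines and the Safety Management Plan, which are not available, may have settled the matter. This stands, and it limits the conclusion to events that may be missed.

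Other parts of the reply also stand:

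- Complications remain reportable in their own right. Hypotension, for example, has its own AESI and SAESI definitions.
- Recurrences are still recorded on their own form and listed (SAP 5.6.1), and those needing intervention before discharge count as failures in a secondary efficacy endpoint (SAP 9.2.2.7). That endpoint does not record instability and stops at discharge rather than Day 5.
- Annex A 5.1.2 speaks broadly of safety data and associated EDC details for Parts B and C. However, 5.1.1 defines the product as a coded AE listing, and 5.2.2 has the reviewer classify AEs.

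Some stronger readings are tempting but unsupported. A reader might count the 18 enrolled PLS subjects, followed for up to 8 months, as exposed to this gap in the endpoint. SAP 9.2.2.13 excludes events before PLS dosing from treatment emergence, only 3 subjects were dosed, and PLS AEs are listed, not tabulated. A reader might treat recurrent AF as one of the drug's main risks; Protocol 1.5 lists ventricular tachycardia, hypotension, bradycardia, sinus pause and 1:1 flutter, not AF recurrence. A reader might conclude that the DSMB was deprived of these events; Protocol 17.3.1 leaves the extent of its review to a charter that is not available.

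**Conclusion.** The contradiction is in the text. Three protocol passages exclude recurrent AF without exception, one protocol passage and two SAP passages would count some of it, and SAP section 10 does not declare the difference. Followed literally, the exclusion removes qualifying events from 24-hour reporting, the AE tables, the sponsor review and the secondary safety endpoint through MLS Day 5.

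How many events were affected, if any, cannot be known from the documents. They give no rate of serious recurrence and do not show which instruction sites followed. A reader might infer that serious recurrences were in fact lost; that is not established. The scale in Step 4 rests on the assumed denominators and on one omitted subject. Since the check is cheap and the endpoint count may be very small, the point should be settled before the safety tables and endpoint are final.

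**What to change.** 1. Reconcile Protocol 9.1 B, 9.1 C and 17.2.1.1 with 9.1.2.4 B and with SAP 3.4 and 5.6.1: recurrent AF is not an AE unless it meets an SAE criterion in 17.2.1.2 or an SAESI criterion in 9.1.2.4 B. Extend the SAP exception to the SAESI criteria too, so that the third row of the table in Step 1 is covered.
2. List the difference in SAP section 10.
3. For data already collected, extend the Annex A 5.1.2 listing to the AF-recurrence records. Screen them against both sets of criteria before the safety tables and endpoint are finalised. The documents do not show that the recurrence form holds hospitalisation or cardioversion fields, so the screen will need concomitant-therapy data and, where these do not settle a case, site queries.

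The cost is a sentence in each affected section, one extra listing and a few queries. The serious-event count may rise slightly. New wording cannot restore 24-hour reporting for MLS subjects, the last of whom was dosed on 07 December 2021; for them the screen in item 3 is the useful part. Nothing here changes treatment.
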